survival (EFS) and overall survival (OS) rates of 81% and 80%, respectively. Ponatinib can be associated with cardiovascular toxicity, including arterial and thromboembolic events; however, using risk-adapted dosing schedule of ponatinib may reduce this risk. Historical comparisons suggest the results achieved with the combination of hyper-CVAD plus ponatinib may be superior to those achieved with hyper-CVAD plus dasatinib.

Venetoclax: Venetoclax (formerly ABT-199/GDC-0199) is a potent, selective and orally bioavailable small molecule BCL-2 inhibitor that has shown promising anti-leukemia activity in patients with relapsed or refractory chronic lymphocytic leukemia (CLL) as monotherapy and modest single agent activity in select subtypes of acute myeloid leukemia ¹²⁻¹⁴; venetoclax is currently FDA approved for the treatment of patients with CLL with del(17)(p13.1) by interphase cytogenetics who have received at least one prior therapy. For patients with AML, combination therapy with venetoclax and other agents appears to be more efficacious that venetoclax monotherapy. ¹⁵ BCL-2 is an anti-apoptotic protein that is over-expressed in many hematologic malignancies and is associated with tumor initiation, disease progression and drug resistance. ¹⁶ BCL-2 mRNA is highly expressed in multiple subtypes of ALL compared with normal pre-B controls. ¹⁷ Recent reports demonstrated that primary B-lineage ALL cells each express high levels of BCL-2 and exhibit significant sensitivity to BCL-2 inhibition by venetoclax, resulting in rapid apoptotic cell death. ¹⁸ Specifically, Ph+ ALL appears to be dependent on BCL-2 for survival; consequently, BCL-2 inhibition has been shown to result in apoptosis of Ph+ ALL cell lines. ¹⁹

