6.3 Follow-up

Thirty days after last dose of the study drugs concomitant medication and AE assessment will be recorded. This may be done over the phone with a member of the study staff.

Patients discontinued from study treatment for any reason other than withdrawal of consent for treatment will continue to be assessed for survival. Survival information (i.e. the date and cause of death) and subsequent treatment will be collected via telephone calls and/or clinical visits every 6 months (+/- 2 months) until death or withdrawal of consent.

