7.2. EVALUATION OF TOXICITY

- Toxicities will be graded according to the NCI Common Toxicity Criteria for Adverse Event Reporting Version 4.0. The toxicity of the regimen will be monitored continuously during the course of the study.
- 2. AEs will be recorded in the subject's source documents from the first dose through 30 days after the last dose. Serious Adverse Events (SAEs) will be captured from the time of the first protocol-specific intervention. The Principal Investigator will sign and date the Adverse Event Record (AE logs) per patient after the completion of each course. Following signature, the AE logs will be used as source documentation for the adverse events for attribution.

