7.3. CRITERIA TO STOP TREATMENT

- Failure to achieve CR/CRi after 2 cycles of treatment, unless the patient is deemed to be deriving clinical benefit (e.g. blast reduction not meeting criteria for CR/CRi) as assessed by the treating physician and PI
- 2. Unacceptable toxicity judged to be related to therapy by the investigator, as defined by the NCI Common Toxicity Criteria (irreversible or prolonged (> 42 days) grade 4 hematological toxicity or grade 4 non-hematological toxicity thought to be related to ponatinib or venetoclax), unless it has been been judged by the treating physician and PI that the patient is achieving clinical benefit.
- 3. Non-compliance by the patient with protocol requirements or patient's request to be removed from the study.
- Relapse, defined as >5% bone marrow blasts not attributed to hematopoietic recovery, occurring after initial response to therapy

Patients coming off treatment due to the above issues will continue to be followed for survival outcomes.

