Important medical events that may not result in death, be life-threatening, or require hospitalization may be considered a serious adverse drug experience when, based upon appropriate medical judgment, they may jeopardize the patient or subject and may require medical or surgical intervention to prevent one of the outcomes listed in this definition. Examples of such medical events include allergic bronchospasm requiring intensive treatment in an emergency room or at home, blood dyscrasias or convulsions that do not result in inpatient hospitalization, or the development of drug dependency or drug abuse (21 CFR 312.32).

Important medical events as defined above, may also be considered serious adverse
events. Any important medical event can and should be reported as an SAE if deemed
appropriate by the Principal Investigator or the IND Sponsor, IND Office.

All events occurring during the conduct of a protocol and meeting the definition of a SAE must be reported to the IRB in accordance with the timeframes and procedures outlined in "The University of Texas M. D. Anderson Cancer Center Institutional Review Board Policy for Investigators on Reporting Unanticipated Adverse Events for Drugs and Devices". Unless stated otherwise in the protocol, all SAEs, expected or unexpected, must be reported to the IND Office, regardless of attribution (within 5 working days of knowledge of the event).

- All life-threatening or fatal events, that are unexpected, and related to the study drug, must
 have a written report submitted within 24 hours (next working day) of knowledge of the event
 to the Safety Project Manager in the IND Office.
- Unless otherwise noted, the electronic SAE application (eSAE) will be utilized for safety reporting to the IND Office and MDACC IRB.
- Serious adverse events will be captured from the time of the first protocol-specific
 intervention, until 30 days after the last dose of drug, unless the participant withdraws
 consent. Serious adverse events must be followed until clinical recovery is complete and
 laboratory tests have returned to baseline, progression of the event has stabilized, or there
 has been acceptable resolution of the event.
- Additionally, any serious adverse events that occur after the 30 day time period that are
 related to the study treatment must be reported to the IND Office. This may include the
 development of a secondary malignancy.

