10. STATISTICAL METHODOLOGY

This is a single arm, open label, phase I/II study to assess the MTD and the efficacy of the combination regimen of venetoclax, ponatinib and corticosteroids in patients with relapsed/refractory Ph+ ALL.

Phase I: The primary objective is to determine the optimal dosing and schedule of the combination regimen. This aim will consist of a phase I trial to determine the maximum tolerated dose (MTD) of venetoclax when given in combination with ponatinib and dexamethasone. A standard 3+3 dose escalation design will be employed: Two dose levels of venetoclax will be explored. Patients will be treated in cohorts of size three to six and the dosage will be escalated if the clinical toxicity is acceptable. A dose-limiting toxicity (DLT) is defined in "Definition of DLT" in section 4.8.

The design is constructed to reduce the chance of escalating the dose when the probability of DLT is high, and increase the chance of escalating the dose when the probability of DLT is low. The MTD is defined as the highest dose level where a DLT occurs within at most one out of six patients treated. The escalation scheme is as follows:

- (1) If none of the initial three patients in a cohort experiences a DLT, then a new cohort of three patients will be treated at the next higher dose level.
- (2) If one of the three patients in a cohort experiences a DLT, then up to three additional patients will be treated at the same dose. Escalation will continue if only one of the six patients experiences DLT.
- (3) If two or more patients in a cohort experience DLT, then the MTD will have been exceeded, and no further dose escalation will occur. The previous dose level will be considered the MTD.
- (4) If only three patients were treated at a dose level under consideration as the MTD, then up to three additional patients will be accrued. If no more than one of the six patients at that dose level experience a DLT, then that dose level will be confirmed as the MTD. If two or more patients in that cohort experience DLT, then the previous dose level will be studied in the same fashion.

The MTD is defined as the highest dose studied for which the observed incidence of DLT is less than 33%. Frequencies of toxicities will be tabulated according to the NCI Common Toxicity Criteria. Patients will be continued to be followed for one year for evidence of late toxicity.

Table 1 below gives the probabilities of dose escalation based on true DLT risk in the 3+3 design.

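### Section 10 states one year of follow-up for late toxicity, but scheduled adverse event collection ends 30 days after the last dose, so late toxicity in patients who stop early can go unrecorded

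*Combined protocol and SAP*

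**What the plan says.** Section 10, at the end of the Phase I text, states: "Patients will be continued to be followed for one year for evidence of late toxicity". It gives no starting point for the year and does not say whether phase II patients are included.

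The operational sections set a shorter window:

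- Section 6.3 schedules one toxicity contact after treatment, which may be by telephone: "Thirty days after last dose of the study drugs concomitant medication and AE assessment will be recorded".
- Section 7.2 uses the same limit: "AEs will be recorded in the subject's source documents from the first dose through 30 days after the last dose".
- Section 8 captures SAEs from the first protocol-specific "intervention, until 30 days after the last dose of drug, unless the participant withdraws" consent. It then adds that "any serious adverse events that occur after the 30 day time period that are" related to study treatment must still go to the IND Office, with no end date.
- For longer follow-up, Section 6.3 says: "Survival information (i.e. the date and cause of death) and subsequent treatment will be collected via telephone calls and/or clinical visits every 6 months", with a tolerance of 2 months either way. No toxicity item is listed.

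Several routes lead out of treatment early. Section 7.3 lists non-response ("Failure to achieve CR/CRi after 2 cycles of treatment, unless the patient is deemed to be deriving clinical benefit"), unacceptable toxicity and relapse. Section 4.2 takes patients off study at allogeneic transplant (ASCT) and follows them for survival.

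**The concern.** The statistical section states a follow-up that the data-collection sections do not deliver. Staff working from Sections 6.3 and 7.2 would comply fully and still not carry out the one-year follow-up.

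The safety of the combination is a secondary objective, and the Introduction acknowledges a vascular risk: "Ponatinib can be associated with cardiovascular toxicity, including arterial and thromboembolic events". Under the plan as written, how long a patient is asked about toxicity depends on how long that patient stays on treatment. The gap is therefore largest in those who stop for toxicity, non-response, relapse or transplant. Few late events in that group could mean that few occurred, or that nobody asked, and the data could not tell these apart.

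**Working it through.** The plan gives no figure to reproduce here. The check sets the sections side by side and counts days.

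**What is asked, and when**

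| Period | Scheduled toxicity question | Other route |
|---|---|---|
| First dose to last dose | Yes, before each cycle (Section 6.2) | SAE reporting (Section 8) |
| Last dose to day 30 after it | Yes, one contact at day 30 (Section 6.3) | SAE reporting (Section 8) |
| After day 30 | None | Related SAEs if the site learns of them (Section 8); cause of death (Section 6.3) |

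The study calendar in Section 6.2 has one Follow-Up column. It marks AE assessment and concomitant medication as well as survival status, without giving times. Section 6.3 assigns AE assessment and concomitant medication, as a pair, to the 30-day contact. That is the natural reading of those marks. EKG and echocardiogram/MUGA have no mark in that column.

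**Inputs for the day count**

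- Cycle 1 lasts 35 days with the 7-day ponatinib lead-in and 28 days without it (Section 4.2).
- Later cycles last 28 days (Section 4.2).
- AE collection runs to 30 days after last dose (Sections 6.3 and 7.2).

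**Formulas**, for c completed cycles without interruption:

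- Last dose day = 28 × c, plus 7 with the lead-in.
- End of AE window = last dose day + 30.
- Uncovered days, year from first dose = the larger of 0 and 365 − end of window.
- Uncovered days, year from last dose = 365 − 30.

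**Year from first dose**

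| Cycles | With lead-in: window ends | Uncovered | Without lead-in: window ends | Uncovered |
|---|---|---|---|---|
| 2 | 63 + 30 = day 93 | 272 (75%) | 56 + 30 = day 86 | 279 (76%) |
| 4 | 119 + 30 = day 149 | 216 (59%) | 112 + 30 = day 142 | 223 (61%) |
| 11 | 315 + 30 = day 345 | 20 (5%) | 308 + 30 = day 338 | 27 (7%) |
| 12 | 343 + 30 = day 373 | 0 | 336 + 30 = day 366 | 0 |

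**Year from last dose:** 365 − 30 = 335 days, or 335/365 = 92%, for every patient however long treated.

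**The case against.** The strongest reply is that the safety net after day 30 is not empty. A late arterial event that is serious and judged related must be reported whenever the site learns of it, and cause of death is collected every 6 months. This stands. A reader might infer that toxicity collection stops altogether at 30 days and that late vascular events are missed. Section 8 does not support that. What can be lost is narrower: non-serious late toxicity (although Section 8 wants related events of any grade in the case report form), serious events judged unrelated, and related SAEs that no scheduled contact brings to light. The request in Section 9 that home physicians report life-threatening events concerns participation during treatment and does not fill the gap.

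Three further limits stand:

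- A reader might take vascular events to be a delayed effect or the principal ponatinib risk. The Introduction says neither. It notes the association and adds that risk-adapted dosing may lessen it.
- A reader might infer that a planned one-year toxicity result is lost. The Analysis Plan in Section 10 contains none; it lists toxicity frequency tables. The safety objective is worded as preliminary, dose-limiting toxicity is judged on cycle 1, and the phase II toxicity stopping rule counts events only while the patient is on study. No primary endpoint or decision rule is affected.
- A reader might assume that the sentence binds every patient. It sits in the Phase I text, which covers 6 to 12 patients, and its reach into phase II is unclear.

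It can also be said that the 2-cycle figure is selective. Section 7.3 lets patients who derive benefit continue, and Section 4.3 allows up to 24 maintenance cycles. That is why the gap is shown by number of cycles.

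**Conclusion.** The inconsistency is real and worth correcting. Section 10 states a one-year late-toxicity follow-up, scheduled collection ends 30 days after last dose, and what remains afterwards is passive reporting of related SAEs plus cause of death. Late toxicity in early leavers can go unrecorded; the documents do not show that it will.

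The size depends on a starting point the plan does not give. From first dose, the gap is 272 (279 without the lead-in) of 365 days after 2 cycles, 216 (223) after 4, and none after 12. From last dose, it is 335 of 365 days for everyone. These counts assume uninterrupted cycles and dosing to the last day of the final cycle. Interruptions that lengthen time on treatment shrink the first-dose gap and leave the last-dose gap unchanged. They are calendar days without a scheduled question, not estimates of events lost. The consequence is confined to the secondary safety description.

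**What to change.** Reconcile Sections 6.3, 7.2, 8 and 10 in one of two ways.

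1. **If one-year follow-up is intended.** State in Section 10 when the year starts and whether it covers phase I patients only or all patients. In Section 6.3, add to the existing 6-monthly contacts within that year a scheduled question on treatment-related events that are serious or grade 3 or higher, naming arterial and venous events. Ask it of everyone the year covers, including patients who have had ASCT. Record any ASCT or subsequent therapy alongside, so that attribution can be judged. Align the windows in Sections 7.2 and 8, and give the Follow-Up marks in the Section 6.2 calendar explicit times.
2. **If it is not intended.** Delete the sentence in Section 10 and report safety as covering treatment plus 30 days only.

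The first option costs a short item on about two calls per patient that are already planned, with a little data entry: at most 12 × 2 = 24 calls if only phase I patients are covered. Its main drawback is that attribution to study drug becomes harder after ASCT or later therapy. The second costs only an edit, but gives up systematic information on late toxicity in patients who stop early.

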4. TREATMENT OF SUBJECTS

- 4.1. Variations in doses of the study agents or supportive care medications or dose schedules other than those suggested below are allowed if deemed to be in the best interest of patients. Such changes should be discussed with the principal investigator before they are instituted.
- 4.2. Treatment Overview The regimen consists of 4 cycles of induction/consolidation followed by up to 2 years of maintenance therapy for responding patients. For patients who have not received ponatinib within 2 weeks of the anticipated start date, the first cycle is 35 days, as single-agent ponatinib will be given for 7 consecutive days, after which venetoclax, ponatinib and corticosteroids will be given in combination. For patients who have received ponatinib within 2 weeks of the anticipated start date, the first cycle is 28 days, as the ponatinib single-agent lead-in will be omitted. For all patients, each consecutive cycle will be 28 days. Patients achieving remission will be referred to ASCT at the discretion of the treating physician, based on donor availability and suitability for ASCT. Patients will be removed from the study and will discontinue venetoclax at the time of ASCT. These patients will still be followed for survival analyses.
- **4.3** Cycle 1 (Induction) Patients who have not received ponatinib within 2 weeks of the anticipated start date will receive the following agents:
 - Ponatinib 45mg orally daily on days 1-35
 - Venetoclax orally in a daily dose escalation schema:

•							
		Day 8	Day 9	Day 10	Day 11	Day 12	Day 13-35
	Dose level -1 venetoclax	20 mg	50 mg	100 mg	200 mg	200 mg	200 mg
	Dose level 1 venetoclax (STARTING DOSE)	20 mg	50 mg	100 mg	200 mg	400 mg	400 mg
	Dose level 2 venetoclax	20 mg	50 mg	100 mg	200 mg	400 mg	800 mg

- Dexamethasone 40mg IV/PO on days 8-11
- CNS prophylaxis with methotrexate 12 mg intrathecally (IT) (6 mg via Ommaya reservoir) on day 9 (± 3 days) and cytarabine 100 mg IT on day 14 (± 3 days).
- For patients with CD20 expression (≥20% by flow cytometry), rituximab 375 mg/m² may be added at the discretion of the treating physician after the maximum dose of venetoclax has been reached. Rituximab will be given on day 14 (±3 days) and on day 21 (±3 days).

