					T	rue DLT ra	ate		
	10%	20%	30%	40%	50%	60%	70%	80%	90%
Probability of									
escalation	0.91	0.71	0.49	0.31	0.17	0.08	0.03	0.01	0.001

A minimum of 6 patients and a maximum of 12 patients will be enrolled to the phase I portion of the trial.

Phase II: The primary objective is to determine the overall response rate, defined as the rate or CR + CRi occurring at the end of 2 cycles of treatment. A total of up to 26 patients will be in the phase II part including patients who received the MTD dose level in the phase I portion and those enrolled in the phase II portion of the study. The target overall response (OR) rate is 60%. This regimen of the combination treatment will be considered worthy of further investigation if it elicits an increase in OR to 60% with

acceptable toxicity. A >15% drug-related grade 4-5 toxicity rate is considered unacceptable. Thus, interim monitoring rules, assuming the prior distributions below, were constructed that meet the following two conditions,

- 1) Stop if $Prob[p(OR, E) < 0.60 \mid data] > 0.975$, or
- 2) Stop if $Prob[p(TOX, E) > 0.15 \mid data] > 0.8$,

where p(OR, E) and p(TOX, E) are the true OR and toxicity rates for the combination treatment. The first rule provides for stopping the study if the data suggest that it is unlikely (i.e., probability < 2.5%) that OR rate of the combination treatment is greater than 0.6. The second condition will stop the study early if excessive therapy-related grade 4-5 toxicity (>15%) is highly probable (i.e., probability >80%) for the combination treatment. Monitoring for toxicity and futility will not begin until 6 patients have been evaluated, and cohort size for future evaluations is 2.

The monitoring rule for the toxicity rate, based on these assumptions and monitoring conditions above is found in Table 2. For example, accrual will cease if 2 or more patients experience toxicities among the first 6 patients. Toxicities will be continually monitored and will count towards this stopping rule if they occur while the patient is still on study.

Table 2. Stop accrual if there are this many drug-related grade 4-5 toxicities among the number of patients evaluated					
# patients evaluated	# patients with toxicities				
6	2-6				
8-10	3-10				
12-16	4-16				
18-20	5-20				
22-24	6-24				
26	Stop due to maximum sample size				

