Monitoring the OR rate, based on the above assumptions and monitoring conditions is found in Table 3. For example, accrual will cease if no patients experience an overall response in the first 6 patients treated.

Table 3. Stop accrual if there are th number of patients evaluated	is many response (i.e., # patients with overall response) among the	
# patients evaluated	# patients with overall response	
6	0	
8	0-1	
10	0-2	
12	0-3	
14	0-4	
16	0-5	
18	0-6	
20	0-7	
22	0-8	
24	0-9	
26	Stop due to maximum sample size	

Multc Lean Desktop (version 2.1.0) was used to generate the toxicity and futility stopping boundaries and the operating characteristics table (Table 3). In order to utilize the software for the design, a 60% constant rate and beta (1.2, 0.8) priors were assumed for the standard treatment response rate and experimental treatment response prior distribution, respectively. In addition, a 15% constant rate and beta (0.3, 1.7) priors were assumed for the standard treatment toxicity rate and experimental treatment toxicity prior distribution, respectively.

The probability of stopping the study early if the true OR of the combination treatment was 60% and the true toxicity rate was 15% was 39.24%. Probabilities of stopping early for high true toxicity rates (i.e., 40%) were 98.27% when the true OR was 60% and 99.79% when true OR rate was 30%.

True Toxicity Rate	True OR	Prob(stop the trial early)
0.10	0.30	0.9028
	0.40	0.6445
	0.50	0.3561
	0.60	0.2064
	0.70	0.1688
0.15	0.30	0.9256
	0.40	0.7278
	0.50	0.5070
	0.60	0.3924
	0.70	0.3636
0.2	0.30	0.9506
	0.40	0.8193
	0.50	0.6727
	0.60	0.5966
	0.70	0.5775
0.3	0.30	0.9861
	0.40	0.9490
	0.50	0.9076
	0.60	0.8861
	0.70	0.8808
0.4	0.30	0.9979
	0.40	0.9922
	0.50	0.9860
	0.60	0.9827
	0.70	0.9819

Secondary objectives include: the rate of minimal residual disease negativity by PCR for BCR-ABL1 transcripts, proportion of patients proceeding to ASCT, relapse-free survival, overall survival, and the safety of the combination regimen.

The investigator is responsible for completing toxicity/efficacy summary reports and submitting them to the IND office Medical Affairs and Safety Group for review. These should be submitted as follows:

- Phase I: A toxicity summary must be submitted after the first 3 evaluable patients, complete 1
 cycle of study treatment, and every 3 evaluable patients thereafter, IND office approval must be
 obtained prior to advancing/changing dose levels.

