Sample Size: We will treat up to 26 patients at the recommended phase II dose (including patients who received the MTD dose level in the phase I portion and those enrolled in the phase II portion of the study). For the efficacy endpoint, with a sample size of 26 patients, If the study is not stopped early and 26 patients have been treated and evaluated in the study, assuming 16 of the 26 patients achieve OR, then the 95% credible interval for OR rate will be (0.43,0.79).

Approximately 10 patients per year are expected to be enrolled. The total study duration is expected to be 5 years (3 years of new patient enrollment, plus an additional 2 years of follow-up).

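### The phase I ceiling of 12 fits dose levels 1 and 2 only; if level -1 is opened after level 2 has failed, the escalation rules can call for 15 or 18 patients

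*Combined protocol and SAP*

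**What the plan says.** All references are to the combined protocol and SAP.

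- Section 10, Phase I, gives the number of levels: "Two dose levels of venetoclax will be explored". It then gives the enrolment limits: "A minimum of 6 patients and a maximum of 12 patients will be enrolled to the phase I portion of the trial".
- The cycle 1 dose table in section 4.3 has three rows. Level 1 is marked as the starting dose, level 2 lies above it, and below it is "Dose level -1 venetoclax".
- Rules (1) to (3) of section 10 are a standard 3+3. A level with 0/3 DLTs escalates. A level with 1/3 is extended by at most three patients and escalates on 1/6. Two or more DLTs mean that the level is too high and the one before it is taken as the MTD.
- Rule (4) extends a candidate MTD that has only three patients, and confirms it if no more than one of six has a DLT. Otherwise: "If two or more patients in that cohort experience DLT, then the previous dose level will be studied in the same fashion".
- Section 10 defines the MTD twice: once as the highest level with at most one DLT in six patients, and again after the rules: "The MTD is defined as the highest dose studied for which the observed incidence of DLT is less than 33" per cent.
- Section 4.7 starts phase II once an MTD is established, or if none is reached at the top venetoclax level.
- Under the reporting requirements in section 10, IND office approval must be "obtained prior to advancing/changing dose levels".

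**The concern.** The ceiling and the count of two levels agree with each other, but not with a dose table that has a third row and a rule that steps down. Rules (1) to (4) never name level -1, and no section says whether its patients count toward the 12.

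Where the two provisions collide, the team would have to choose, with the DLT data in hand, between exceeding a stated enrolment limit and leaving rule (4) unfinished. The second choice can leave phase I without a confirmed MTD while a listed lower level is untested or has only three patients. It would then be debatable whether the phase I primary objective was met, and which dose, if any, phase II inherits.

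**Working it through.** **Inputs.** Levels -1, 1 (start) and 2 from the section 4.3 table; rules (1) to (4), the limits of 6 and 12 and the two MTD definitions from section 10. Assumptions: full cohorts of three evaluable patients, and level -1 taken as the level before level 1. True DLT rates are not in the documents and are varied below.

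**The plan's own figures first.** Table 1 of section 10 follows from P(escalate) = (1-p)³ + 3p(1-p)²·(1-p)³. At p = 0.30 this is 0.343 + 0.441 × 0.343 = 0.494, against 0.49 stated; all nine entries reproduce. With levels 1 and 2 only, the rules give totals of 3, 6, 9 or 12. The stated maximum of 12 therefore reproduces as 2 × 6.

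**With level -1 added**, the possible totals are 6, 9, 12, 15 and 18. If level 1 fails before level 2 opens, the total is at most 6 + 6 = 12. A total above 12 arises only after this sequence: level 1 0/3; level 2 fails; level 1 is extended and its added three have two or more DLTs. The branches are:

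| Level 2 failed in | Used when level -1 opens | Result at level -1 | Total |
|---|---|---|---|
| 3 | 3 + 3 + 3 = 9 | ≥2 DLTs in 3 | 12, within the ceiling |
| 3 | 9 | 0/3 or 1/3, extended to 6 | 15 |
| 6 | 3 + 6 + 3 = 12 | ≥2 DLTs in 3 | 15 |
| 6 | 12 | 0/3 or 1/3, extended to 6 | 18 |

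**One case by hand**, assumed DLT rates 20/30/40% at levels -1/1/2:

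- Level 1 0/3: 0.7³ = 0.343. Two or more DLTs in its added three: 3 × 0.09 × 0.7 + 0.027 = 0.216. Product 0.0741.
- Level 2 fails in three: 3 × 0.16 × 0.6 + 0.064 = 0.352. Level 2 passes (at most 1/6): 0.6⁶ + 6 × 0.4 × 0.6⁵ = 0.233. It fails in six: 1 - 0.352 - 0.233 = 0.415.
- Two or more DLTs in three at level -1: 3 × 0.04 × 0.8 + 0.008 = 0.104.
- P(total > 12) = 0.0741 × (0.352 × 0.896 + 0.415) = 0.054.

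**Across assumed rates** (percentages):

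| DLT rates at -1/1/2 | Rules need >12 | All 12 used before -1 opens | Level -1 cut off at 3 by the ceiling |
|---|---|---|---|
| 10/10/10 | 0.2 | 0.18 | 0.06 |
| 5/10/15 | 0.5 | 0.33 | 0.12 |
| 5/10/20 | 0.7 | 0.49 | 0.21 |
| 10/15/25 | 1.7 | 1.16 | 0.57 |
| 15/25/40 | 4.9 | 2.73 | 2.18 |
| 20/30/45 | 5.9 | 3.05 | 2.82 |
| 25/35/50 | 6.3 | 3.02 | 3.26 |
| 20/40/60 | 6.8 | 2.36 | 4.41 |

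**Upper bound for any rates.** P(total > 12) ≤ (1-p)³ × [3p²(1-p) + p³], with p the level 1 rate. The maximum is near p = 0.36: 0.2621 × 0.2955 = 0.0775 (0.07746 unrounded, or 7.7%).

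**If the ceiling is applied.** With 12 used, levels 1 and 2 have both failed and level -1 is not opened. With 9 used, level -1 stops at three patients. A result of 1/3 is 33.3% and meets neither MTD definition. A result of 0/3 is below 33% but lacks the six patients that rule (4) requires; it makes up 50% to 86% of the cut-off cases in the last column.

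**Early closure.** The rules set three as the most that may be added. If a cohort may close at its second DLT, totals can be lower, for example 3 at level 2 + 5 at level 1 + 6 at level -1 = 14, which is still above 12. The split between 9 used and 12 used holds only for full cohorts.

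**The case against.** The best defence is that section 10 is consistent with itself: two levels, six patients each, twelve in all. Level -1 lies below the starting dose, the rules never name it, and the term for the preceding level is not defined for the starting level. That stands as a caveat: the step-down to level -1 is an inference. It does not remove the point, because the row sits in the table as an assignable level and no other purpose for it is evident.

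A reader might infer that the plan is silent on what happens at the ceiling. The documents do not support that. A maximum stops enrolment, and section 4.7 does not start phase II unless an MTD is established or the top level is cleared. With levels 1 and 2 both failed and level -1 unopened, neither condition is met. What stays unclear is 0/3 at level -1.

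A reader might also infer that any use of level -1 breaks the ceiling, or that the ceiling and rule (4) conflict on the whole route. Neither is right. Level -1 opens straight from a failed level 1 in 9% to 69% of trials under the tabulated rates, always within 12, and only 2% to 11% of all level -1 openings exceed the ceiling. One branch of the route itself ends at exactly 12.

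Nor is this a safety gap. Reaching the ceiling stops enrolment, and the IND office must approve each change of dose level. That approval does not, however, settle whether level -1 counts toward the 12. Section 4.8 lets the principal investigator call for further patients at a level on safety grounds, but does not mention the ceiling either.

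**Conclusion.** The point holds as a minor inconsistency in a stated figure. The maximum of 12 matches levels 1 and 2; it does not match a three-row dose table combined with rule (4), under which 15 or 18 patients can be needed on most branches of one route. The chance is about 0.2% to 7% under the assumed rates and at most 7.7% for any rates. These figures rest on full cohorts, evaluable patients, and the reading of level -1 as the level before level 1. Allowing cohorts to close early lowers some totals without removing the excess. The stated minimum of 6 is not disputed.

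**What to change.** Reconcile the section 4.3 dose table with the number of levels, rule (4) and the enrolment limits in section 10, so that the ceiling matches the rules. Either of two statements would do:

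- **(A)** The phase I maximum is 12 for levels 1 and 2, and up to 18 if level -1 is studied after level 2.
- **(B)** The maximum is 12 including level -1, and phase I ends without a confirmed MTD if 12 is reached before rule (4) is complete.

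In addition, state which of the two MTD definitions in section 10 applies to 0/3 at level -1.

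No dose level, escalation rule or Table 1 entry changes. (A) raises the ceiling by 6 on a route with probability of at most 7.7%. Because the 26 phase II patients include those treated at the MTD in phase I, the trial total on that route could reach 9 + 26 = 35 or 12 + 26 = 38. The Sample Size paragraph says "Approximately 10 patients per year are expected to be enrolled", which makes that 3.5 or 3.8 years, against a planned "3 years of new patient enrollment". Other routes can already reach 6 + 26 = 32 patients, or 3.2 years, so the added effect on the timeline is small. (B) adds no patients but accepts that phase I may end without a confirmed MTD, with about the same small probability.
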